2.1.2 Prior or concomitant medications

All medications taken within 3 months before screening visit (any time for prior SGLT2 use) and until the end of the study are to be reported in the electronic case report form (e-CRF).

All medications will be coded using the World Health Organization-Drug Dictionary using the version currently in effect at Sanofi at the time of database lock.

- Prior medications are those the patient used prior to first administration of the double-blind IMP. Prior medications can be discontinued before first administration or can be ongoing during treatment phase.
- Concomitant medications are any treatments received by the patient concomitantly to the IMP from the first administration of double-blind IMP to the date of the last administration of double-blind IMP + 10 days. A given medication can be classified both as a prior medication and as a concomitant medication.
- Posttreatment medications are those the patient took in the period running from the 11th day after the last administration of double-blind IMP up to the end of the study.

Background metformin is considered as a noninvestigational medicinal product (NIMP). Metformin (commercial formulations) will be administered orally according to the locally approved label.

2.1.2.1 Rescue therapy

Except for SGLT2 inhibitors, any approved medication(s) including oral antidiabetic drugs or insulin can be prescribed at the Investigator's discretion to treat the hyperglycemia. Rescue therapy is considered a NIMP.

2.1.2.2 Prohibited prior and concomitant medications

During the study treatment period, the following medications are prohibited:

- Initiation of any antidiabetic agents, including oral or injectable antihyperglycemic agents other than the IMP is not allowed before the rescue therapy,
- Systemic use of glucocorticoids is not allowed for more than 10 consecutive days (topical, ophthalmic, nasal spray or inhaled applications are allowed),
- Initiation of any weight loss drugs (eg, phentermine, orlistat),
- Investigational medicinal products in any other clinical study,
- SGLT2 inhibitor (eg, canagliflozin, dapagliflozin, or empagliflozin) are not allowed for rescue.

Reduction of digoxin dose should be considered because sotagliflozin acts as a weak P-glycoprotein inhibitor and increases systemic exposure to digoxin.

Other medications which are unlikely to interfere with the pharmacokinetic (PK) or pharmacodynamics (PD) of the IMP or confound interpretation of the study endpoints are allowed as needed following discussion between the Investigator and the Sponsor. However, doses of chronically administered medicines should be kept fixed during the trial if at all possible.

After premature permanent discontinuation of the IMPs, any treatments (other than SGLT2 inhibitors) are permitted, as deemed necessary by the Investigator.

The dose of all antihypertensive agents should be kept constant during the 12 weeks following randomization and no antihypertensive agents should be added or withdrawn for the 12 weeks following randomization unless it is considered necessary for safety reasons.

2.1.3 Efficacy endpoints

All efficacy measurements collected during the study will be considered for analyses, including those obtained after IMP discontinuation or introduction of rescue therapy (see [Section 2.5.4](#)).

Efficacy variables HbA1c, 2-hour PPG, FPG, UACR, UGE, UGCR, serum creatinine, and eGFR will be measured/calculated by a central laboratory (see study flowchart in Appendix H). Body weight, SBP and DBP (see [Section 2.1.4.5](#)) will be measured at on-site visits by the investigator. Patients requiring rescue are identified as those with the reason for treatment ticked “rescue therapy” in e-CRF “Medication” page.

Efficacy variables will be summarized in both standard international units and conventional units when applicable.

2.1.3.1 Primary efficacy endpoint

- Change from Baseline to Week 26 in HbA1c (%).

2.1.3.2 Secondary efficacy endpoints

The continuous secondary efficacy endpoints are:

- Change from Baseline to Week 26 in 2-hour PPG following a MM
- Change from Baseline to Week 26 in FPG
- Change from Baseline to Week 26 in body weight
- Change from Baseline to Week 12 in SBP for patients with baseline SBP ≥ 130 mmHg
- Change from Baseline to Week 12 in SBP for all patients
- Proportion of patients with HbA1c $<6.5\%$, $<7.0\%$ at Week 26.

2.1.3.3 Other efficacy endpoints

- Change from Baseline to Week 12 in SBP for patients with baseline SBP <130 mmHg
- Proportion of patients with reduction in body weight by $\geq 2\%$, $\geq 5\%$, and $\geq 10\%$ from baseline
- Changes from baseline to Week 12 in DBP
- Proportion of patients achieving SBP <130 mmHg for those with baseline SBP ≥ 130 mmHg
- Proportion of patients achieving DBP <80 mmHg for those with baseline DBP ≥ 80 mmHg
- Proportion of patients requiring rescue for hyperglycemia
- Change from Baseline in:
 - UACR, UGE, and UGCR
 - Serum creatinine
 - eGFR
- Change from Baseline to Week 79 in HbA1c
- Change from Baseline to Week 79 in FPG
- Change from Baseline to Week 26 in SBP for all patients and for patients with baseline SBP ≥ 130 mmHg
- Change from Baseline to Week 79 in SBP for all patients and for patients with baseline SBP ≥ 130 mmHg
- Change from Baseline to Week 79 in body weight.

2.1.3.4 ABPM substudy efficacy endpoint(s)

Primary endpoints

The primary endpoint of the substudy is:

- Change from Baseline to Week 12 in average 24-hour SBP in a subset of patients with mean SBP ≥ 130 mmHg at Screening.

Secondary endpoints

The secondary endpoints of the substudy are:

- Change from Baseline to Week 26 in average 24-hour SBP
- Change from Baseline to Week 12 and 26 in average 24-hour DBP
- Change from Baseline to Week 12 and 26 in average adjusted awake time BP as measured by SBP and DBP with adjustment based on actigraphy

- Change from Baseline to Week 12 and 26 in average adjusted sleep time BP as measured by SBP and DBP with adjustment based on actigraphy.

2.1.4 Safety endpoints

The safety analysis will be based on the reported adverse events (AEs), hypoglycemia, and other safety information, such as clinical laboratory data, vital signs, electrocardiogram (ECG), and physical examination, etc.

Observation period

The observation period will be divided into 4 epochs:

- The **screening** epoch is defined as the time from the signed informed consent date up to the first administration of the double-blind IMP.
- The treatment epoch is defined as the time from the first administration of double-blind IMP to the last administration of double-blind IMP. This epoch includes the 26-week double-blind core treatment period and the 53-week double-blind extension treatment period. The 26-week double-blind core treatment period is the time from the first administration of double-blind IMP to the last administration of double-blind IMP on or before Visit 9/Week 26 (or Day 182 if Visit 9/Week 26 date is missing).
- The **residual treatment** epoch is defined as the time from the last administration of double-blind IMP to the last administration of double-blind IMP + 10 days (1 day for hypoglycemia).

The treatment-emergent adverse event (TEAE) period for the 79-week double-blind entire treatment period will include both **treatment** and **residual treatment** epochs (See the TEAE period for the 26-week double-blind core treatment period in [Section 2.5.4](#)).

- The **posttreatment** epoch is defined as the period of time starting the day after the end of the treatment-emergent adverse event period up to the last protocol-planned visit or the resolution/stabilization of all serious adverse events (SAE), adverse events of special interest (AESI) and events of special interest (EOSI), whichever is later.

The on-study observation period is defined as the time from start of double-blind treatment until the end of the study (defined as the last scheduled visit for those who completed the study and the date collected on e-CRF page “Completion of End of Study/Follow-up” for those who did not complete the study).

The post-study observation period is defined as the time from the day after the end of the study until the resolution/stabilization of all SAE, AESI and EOSI if applicable.

2.1.4.1 Hypoglycemia

Hypoglycemia will be identified as events recorded on the dedicated e-CRF “Hypoglycemic Event information” page, and will be categorized as follows (see protocol for further details):

Severe hypoglycemia

Severe hypoglycemia is an event requiring assistance of another person to actively administer carbohydrate, glucagon, intravenous glucose or other resuscitative actions. These episodes may be associated with sufficient neuroglycopenia to induce seizure, unconsciousness or coma.

Self-monitored plasma glucose values may not be available, but neurological recovery attributable to the restoration of plasma glucose to normal is considered sufficient evidence that the event was induced by a low plasma glucose concentration.

Severe hypoglycemia is identified in eCRF “Hypoglycemic Event Information” page as those documented as,

1. To the question “Countermeasure Administration”, ticked the option “Subject was Not Capable of Treating Self and Required Assistance”, and
2. To the question “Were Symptoms Present”, ticked “Yes”.

Documented symptomatic hypoglycemia

Documented symptomatic hypoglycemia is an event during which typical symptoms of hypoglycemia accompanied by a measured plasma glucose concentration of ≤ 3.9 mmol/L (70 mg/dL).

Clinical symptoms that are considered to result from a hypoglycemic episode are eg, increased sweating, nervousness, asthenia/weakness, tremor, dizziness, increased appetite, palpitations, headache, sleep disorder, confusion, seizures, unconsciousness, or coma.

Documented symptomatic hypoglycemia is identified in eCRF “Hypoglycemic Event Information” page as those documented as:

1. To the question “Countermeasure Administration”, NOT ticked the option “Subject was Not Capable of Treating Self and Required Assistance”, and
2. To the question “Were Symptoms Present”, ticked “Yes”, and
3. With a plasma glucose value before countermeasure ≤ 3.9 mmol/L (70 mg/dL).

Asymptomatic hypoglycemia

Asymptomatic hypoglycemia is an event not accompanied by typical symptoms of hypoglycemia but with a measured plasma glucose concentration ≤ 3.9 mmol/L (70 mg/dL).

Asymptomatic hypoglycemia is identified in eCRF “Hypoglycemic Event Information” page as those documented as:

1. To the question “Countermeasure Administration”, NOT ticked the option “Subject was Not Capable of Treating Self and Required Assistance”, and
2. To the question “Were Symptoms Present”, ticked “No”, and
3. With a plasma glucose value before countermeasure ≤ 3.9 mmol/L (70 mg/dL).

Probable symptomatic hypoglycemia

Probable symptomatic hypoglycemia is an event during which symptoms of hypoglycemia are not accompanied by a plasma glucose determination, (but that was presumably caused by a plasma glucose concentration ≤ 3.9 mmol/L [70 mg/dL]), ie, symptoms treated with oral carbohydrate without a test of plasma glucose.

Probable symptomatic hypoglycemia is identified in e-CRF “Hypoglycemic Event Information” page as those documented as,

1. To the question “Countermeasure Administration”, NOT ticked the option “Subject was Not Capable of Treating Self and Required Assistance”, and
2. To the question “Were Symptoms Present”, ticked “Yes”, and
3. With no plasma glucose value before countermeasure, and
4. To the question “Did this countermeasure lead a significant improvement or prompt recovery?” ticked “Yes”.

Relative hypoglycemia

Relative hypoglycemia, recently termed “pseudo-hypoglycemia” is an event during which the patient reports typical symptoms of hypoglycemia, and interprets the symptoms as indicative of hypoglycemia, but with a measured plasma glucose concentration > 3.9 mmol/L (70 mg/dL).

Relative hypoglycemia is identified in eCRF “Hypoglycemic Event Information” page as those documented as,

1. To the question “Countermeasure Administration”, NOT ticked the option “Subject was Not Capable of Treating Self and Required Assistance”
2. To the question “Were Symptoms Present”, ticked “Yes”, and
3. With a plasma glucose value before countermeasure > 3.9 mmol/L (70 mg/dL).

In addition of the threshold of ≤ 3.9 mmol/L (70 mg/dL), hypoglycemia episodes with a plasma glucose of < 3.0 mmol/L (54 mg/dL) will be analyzed separately.

Any hypoglycemic event fulfilling the criteria of a SAE or leading to unconsciousness, coma, or seizure will also be recorded as a SAE ([Section 2.1.4.2](#)).

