10.6.1 Hypoglycemia

During the study, patients are instructed to document any hypoglycemic episodes in their study diary. The hypoglycemia will be reported in the specific e-CRF page with onset date and time, symptoms and/or signs, the SMBG value if available, and the treatment. If the event fulfills SAE criteria, hypoglycemia will also be reported as an SAE.

Hypoglycemia is categorized according to the ADA workgroup on hypoglycemia classification (13, 14) and summarized in [Figure 1](#).

In addition to the threshold of ≤ 3.9 mmol/L (≤ 70 mg/dL), hypoglycemia episodes with a plasma glucose of <3.0 mmol/L (<54 mg/dL) will be analyzed separately.

Figure 1 - Hypoglycemia classification in Study EFC14834

*The patient is not able to treat her/himself because of the acute neurological impairment and requires another person to actively administer sugar, glucagon or intravenous glucose

Severe hypoglycemia

Severe hypoglycemia is an event requiring assistance of another person to actively administer carbohydrate, glucagon, intravenous glucose or other resuscitative actions. These episodes may be associated with sufficient neuroglycopenia to induce seizure, unconsciousness or coma. Self-monitored plasma glucose values may not be available, but neurological recovery attributable to the restoration of plasma glucose to normal is considered sufficient evidence that the event was induced by a low plasma glucose concentration.

Note: “requiring assistance of another person” means that the patient could not help himself or herself to treat the hypoglycemia. Assisting a patient out of kindness, when assistance is not required, should not be considered a “requires assistance” incident.

Any hypoglycemic event which leads to unconsciousness, coma, or seizure should also be reported as an **SAE**.

Documented symptomatic hypoglycemia

Documented symptomatic hypoglycemia is an event during which typical symptoms of hypoglycemia accompanied by a measured plasma glucose concentration of ≤ 3.9 mmol/L (≤ 70 mg/dL).

Clinical symptoms that are considered to result from a hypoglycemic episode are eg, increased sweating, nervousness, asthenia/weakness, tremor, dizziness, increased appetite, palpitations, headache, sleep disorder, confusion, seizures, unconsciousness, or coma.

Asymptomatic hypoglycemia

Asymptomatic hypoglycemia is an event not accompanied by typical symptoms of hypoglycemia but with a measured plasma glucose concentration ≤ 3.9 mmol/L (≤ 70 mg/dL).

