Sustained eGFR <15 mL/min/1.73 m ²	(2) For eGFR <15 mL/min/1.73 m ² , (2a) confirmed eGFR <15 mL/min/1.73 m ² for ≥30 days with no reversible cause as recorded in eCRF “eGFR decrease”, OR (2b) positively adjudicated by CEC: Yes to the question “Does the subject meet the criteria of CKD progression”.
Chronic dialysis	(3) For dialysis, (3a) dialysis lasted for ≥90 days (eg, end date – start date+ 1 ≥90) as recorded in eCRF “Renal Event – Dialysis”, OR (3b) positively adjudicated by CEC: Yes to the question “. Does the subject meet the criteria for ESRD”.
Renal transplant *	(4) “Renal transplant” captured in eCRF “Other procedure form”, where adjudication is not required. PTs of Renal transplant (10038533), Renal and pancreas transplant (10052278), Renal and liver transplant (10052279) based on MedDRA v21.1.
Renal death	(5) Renal death as positively adjudicated by CEC: “Death - Non-Cardiovascular (Renal)” as the primary cause of death
EOSI not adjudicated *	
Severe hypoglycemia	algorithm specified in Section 2.1.4.1 based on eCRF “Hypoglycemic Events”
Genital mycotic infections	PTs in Appendix F
Urinary tract infections	PTs in Appendix F
Clinically relevant volume depletion and events related/possibly related to volume depletion	PTs in Appendix F
Diarrhea	Narrow search on “Noninfectious diarrhoea (SMQ)” [20000218] plus the following PTs (MedDRA v21.1): Gastroenteritis (10017888), Antidiarrhoeal supportive care (10055660), Enteritis (10014866), Enteritis leukopenic (10014877), Enterocolitis (10014893), Enterocolitis haemorrhagic (10014896)
Pancreatitis	PTs in Appendix F
Venous thrombotic events	PTs in Appendix F

Statistical Analysis Plan

Version: 3

Lexicon Pharmaceuticals Protocol No. EFC14834

Date of Issue: 10 December 2019

Covance Study ID: 000000150525

AE Grouping	Criteria
Malignancies of special interest	Breast cancer: Narrow search on "Breast cancer: Narrow search on "Breast neoplasms, malignant and unspecified (SMQ)" [20000149] Prostate cancer: Narrow search on "Prostate neoplasms, malignant and unspecified (SMQ)" [20000152] Leydig-cell cancer: PTs of Leydig cell tumour of the testis (10024407) and Ovarian Sertoli-Leydig cell tumour (10073270) based on MedDRA v21.1 Thyroid cancer: PTs in Appendix F Renal cell cancer: PTs in Appendix F Pancreatic cancer: PTs in Appendix F Bladder cancer: PTs in Appendix F

EOSI AE leading to an amputation

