2.4.5.1 Analyses of hypoglycemia

Analyses of hypoglycemia will be performed on the treatment-emergent AE periods as defined in [Section 2.1.4](#). Hypoglycemia will be classified as severe hypoglycemia, documented symptomatic hypoglycemia, asymptomatic hypoglycemia, probable symptomatic hypoglycemia or relative hypoglycemia [Section 2.1.4](#).

The number (%) of patients with any hypoglycemia, severe hypoglycemia, and documented symptomatic hypoglycemia will be summarized respectively by treatment group during the treatment-emergent AE period, as well as the incidence rate in patient years. Two types of incidence rates will be presented: the number of patients with at least 1 event per 100 patient-years (calculated as the number of patients with at least 1 event / total exposure in 100 patient-years), and the number of events per 100 patient-years (calculated as the total number of events / (total exposure in 100 patient-years)). Note: here exposure in days is duration of treatment-emergent AE period, ie, duration of IMP treatment in days +1 ([Section 2.1.4](#)).

The summary of frequency and incidence rate in patient years for severe hypoglycemia or documented symptomatic hypoglycemia will be provided as appropriate by gender (Male, Female), age group (<50, ≥ 50 to <65, ≥ 65 years) and race (White, Black or African American, Asian, Other).

A KM curve will also be provided by treatment group for the time to first severe hypoglycemia or documented symptomatic hypoglycemia during the treatment-emergent AE period for the 79-week entire treatment period only (see [Section 2.5.4](#)).

Documented symptomatic hypoglycemia maybe presented by ≤ 3.9 mmol/L (70 mg/dL) and < 3.0 mmol/L (54 mg/dL) respectively, as appropriate.

A listing of patients for all events reported on the dedicated eCRF “Hypoglycemic event information” page will be provided with flagged category (ie, severe hypoglycemia, documented symptomatic hypoglycemia, asymptomatic hypoglycemia, probable symptomatic hypoglycemia or relative hypoglycemia).

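### The SAP's coded rule for severe hypoglycaemia adds a symptoms condition absent from the written definition, so an assisted event with symptoms answered No or left blank is placed in no category

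*SAP*

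**What the plan says.** Protocol 10.6.1 gives the written definition: "Severe hypoglycemia is an event requiring assistance of another person to actively administer carbohydrate, glucagon, intravenous glucose or other resuscitative actions". It sets no separate symptoms condition. It also accepts neurological recovery once glucose is restored as sufficient evidence when no glucose value is available. The section refers to Figure 1 for the classification. The figure is not shown in the copy reviewed, but its footnote is: "The patient is not able to treat her/himself because of the acute neurological impairment and requires another person to actively administer sugar".

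SAP 2.1.4.1 repeats the written definition and then gives the e-CRF rule, which has two conditions joined by and:

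- the countermeasure question has "ticked the option “Subject was Not Capable of Treating Self and Required Assistance”, and"
- "To the question “Were Symptoms Present”, ticked “Yes"

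For documented symptomatic, asymptomatic, probable symptomatic and relative hypoglycaemia, the first condition is the reverse: "NOT ticked the option “Subject was Not Capable of Treating Self and Required Assistance".

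SAP Table 3 lists severe hypoglycaemia among the events of special interest that are not adjudicated and identifies it by the "algorithm specified in Section 2.1.4.1". SAP 2.4.5.1 describes the output: "The number (%) of patients with any hypoglycemia, severe hypoglycemia, and documented symptomatic hypoglycemia will be summarized respectively by treatment group". It adds two incidence rates per 100 patient-years, summaries by gender, age and race, a Kaplan-Meier curve of time to first severe or documented symptomatic event, and a listing with the category flagged.

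**The concern.** The coded rule is narrower than the definition that it is meant to implement, and no other category picks up what it leaves out. An event in which the patient could not self-treat and needed help, but whose symptoms question was answered No or not answered, gets no category at all. That holds even with a measured glucose at or below 3.9 mmol/L.

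Severe hypoglycaemia is not in the Clinical Endpoint Committee's remit, so adjudication would not restore such an event. The rule also runs against the SAP's usual caution with incomplete safety data. Under SAP 2.5.3, an event with an incomplete onset date counts as treatment-emergent unless the partial date shows otherwise, and a missing causality assessment is treated as related. Here an incomplete answer removes the event from its category. Severe events are plausible despite the metformin background, because protocol 8.2.2 allows insulin as rescue.

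**Working it through.** The plan gives no figure to reproduce, so the check is to apply the five rules in SAP 2.1.4.1 to every combination of the e-CRF fields that they use.

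**Inputs**

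- Assistance option: ticked or not ticked (2 values)
- Symptoms present: Yes, No or blank (3 values)
- Glucose before countermeasure: at or below 3.9 mmol/L, above 3.9 mmol/L, or none (3 values)
- Prompt recovery after countermeasure: Yes or not Yes (2 values)

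**The five rules**

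| Category | Assistance | Symptoms | Glucose (mmol/L) | Recovery |
|---|---|---|---|---|
| Severe | ticked | Yes | not used | not used |
| Documented symptomatic | not ticked | Yes | ≤3.9 | not used |
| Asymptomatic | not ticked | No | ≤3.9 | not used |
| Probable symptomatic | not ticked | Yes | none | Yes |
| Relative | not ticked | Yes | >3.9 | not used |

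**As written**

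- All combinations: 2 × 3 × 3 × 2 = 36.
- Assisted combinations: 1 × 3 × 3 × 2 = 18.
- Assisted, symptoms Yes: 1 × 3 × 2 = 6, all severe.
- Assisted, symptoms No: 1 × 3 × 2 = 6, in no category.
- Assisted, symptoms blank: 1 × 3 × 2 = 6, in no category.
- Assisted and unclassified: 6 + 6 = 12 of 18.
- No combination falls in two categories.

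If the e-CRF forces a Yes or No answer, which the documents do not say, the blanks disappear. There are then 1 × 2 × 3 × 2 = 12 assisted combinations, of which 6 are severe and 6 are in no category. The gap remains.

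**With the symptoms condition removed from the severe rule**

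- All 18 assisted combinations are severe; none is unclassified.
- No combination falls in two categories.
- The non-assisted combinations are unaffected. Of these 18, 7 are classified and 11 are not, before and after; that is a separate matter.

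**Is there a rule elsewhere that rescues these events?** SAP 2.5.3 covers missing onset dates, dose dates, causality and severity, but not a missing or negative symptoms answer. The unredacted rows of SAP Table 2 do not record the added condition as a change.

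**Where an unclassified assisted event would still appear**

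- Any hypoglycaemia: apparently yes. SAP 2.1.4.1 identifies hypoglycaemia as whatever is recorded on the dedicated e-CRF page, although SAP 2.4.5.1 does not say outright that uncategorised events count.
- The listing: yes, because it covers all events on that page, but without a category flag.
- SAEs: yes, if the event meets SAE criteria or led to unconsciousness, coma or seizure. An assisted event short of these need not be an SAE.

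**The case against.** The strongest reply is that the second condition only codes what the definition already implies. The Figure 1 footnote attributes the inability to self-treat to acute neurological impairment, and confusion, seizures, unconsciousness and coma are all on the symptom list. A correctly completed form for a severe event would normally say Yes. An assisted record with symptoms No is then self-contradictory, and a blank is missing data. Protocol 13.4 requires complete case report forms and provides for queries that the investigator must answer. A symptoms branch in the unseen Figure 1 cannot be excluded either.

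Much of this stands. It confines the exposure mainly to incomplete or inconsistent forms, and it bars the flat statement that the SAP contradicts the whole of the protocol's classification. It does not close the gap. The general query process does not guarantee that every such record is resolved, and the SAP has no rule for one that is not. Even if Figure 1 has a symptoms branch, the SAP would still give these events no category.

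A second reply is that dropping the condition is too broad, because it would make severe an assisted event with symptoms No and glucose above 3.9 mmol/L. The downside is real but limited. The coded severe rule already ignores glucose, so it already admits an assisted event above 3.9 mmol/L when symptoms is Yes. The e-CRF option itself requires incapacity to self-treat, and protocol 10.6.1 excludes help given when it was not needed.

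Three stronger readings are tempting and are not supported:

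- A reader might infer that these events vanish from the safety report. They appear to stay in any hypoglycaemia and in the listing, and the serious ones also among the SAEs.
- A reader might infer a separate loss from an event-of-special-interest table. SAP 2.4.5.2 places severe hypoglycaemia within the hypoglycaemia summary and describes no such table for it.
- A reader might turn 12 of 18 into a share of events lost. It counts logical combinations. The documents give neither an expected number of severe events nor a rate of incomplete symptom answers.

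**Conclusion.** The point holds as a mismatch between the coded rule and the written definition, with a gap in the classification: 12 of 18 assisted field combinations fall in none of the five categories. An affected event would be missing from the severe count, both incidence rates for severe events, the subgroup summaries by gender, age and race, and the time-to-first-event curve. The direction is under-counting of an event of special interest.

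The number of events at risk cannot be estimated from the documents and may be zero if every form is complete and consistent. The safety analysis is descriptive, so no hypothesis test depends on it. The conclusion rests on the written definition in protocol 10.6.1 and the SAP's prose, with Figure 1 not available. It is worth correcting before database lock because the correction is small and, if severe events are few, one unclassified record would be visible in the count.

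**What to change.** In SAP 2.1.4.1, remove the symptoms condition from the severe rule, so that the assistance tick alone classifies an event as severe. Add a sentence that every assisted record with symptoms No or blank will be queried before database lock, and that any still unresolved will be listed. Check the result against protocol Figure 1 and record the change in SAP Table 2.

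The cost is one line of rule text and the matching code, one added sentence, and a targeted query. The downside is that an assistance box ticked in error counts as severe unless the query corrects it. That error can be seen on the record and listed.
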